3.7 Definitions of Outcomes

Primary and secondary endpoints, including adverse events, will be collected, measured, calculated, and pre-defined according to the study design.

- Composite neonatal morbidity and mortality (NMI): neonatal morbidity and mortality (14). Neonates are assigned points according to the following criteria.
0 to 4 scale with NICU
 - 0 = no events,
 - 1 = one event for (RDS, BPD, grade III or IV IVH, PVL, proven sepsis, or NEC) or <5 days in the NICU, and no perinatal mortality;
 - 2 = two events or between 5 and 20 days in the NICU, and no perinatal mortality;

3 = three or more events or >20 days in the NICU, and no perinatal mortality;

4 = perinatal mortality

The component condition abbreviations are defined as follows:

RDS: respiratory distress syndrome

BPD: bronchopulmonary dysplasia

IVH: intraventricular hemorrhage

NEC: necrotizing enterocolitis

PVL: periventricular leukomalacia

Component conditions are further defined in Appendix 1.

- Length of neonatal hospital stay (NNOLOS): days from delivery to neonatal discharge home, or until death if occurring before discharge. This includes all levels of care before discharge home, including all transfers across levels of care. NNOLOS will be calculated in fractional days if times of birth and discharge are available and rounded to the nearest integer, or as the number of days of difference between dates if times are not available; times are not required. In cases of stillbirth or neonatal mortality prior to discharge home, NNOLOS is set to one day longer than the maximum length of stay recorded for any infant. NNOLOS will be truncated at $44^{0/7}$ weeks of gestational age as specified in the protocol.

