- Length of neonatal NICU stay (NICULOS): days from admission to neonatal intensive care (NICU) to neonatal discharge home from the NICU or until death if occurring before discharge. This includes all levels of care designated by ChristianaCare as intensive care, including all transfers across levels of intensive care. Nursery and non-intensive care days are not included. This will be calculated in fractional days if times of admission and discharge are available and rounded to the nearest integer value of total days, or as the number of total days in intensive care if times are not available; times are not required. NICULOS is set to zero for babies never admitted to the NICU but admitted to the hospital. In cases of stillbirth or neonatal mortality in the NICU, NICULOS is set to one day longer than the maximum length of stay recorded for any infant. NICULOS will be truncated at $44^{0/7}$ weeks of gestational age as specified in the protocol.

- Duration of gestation: GAB is set to $40^{0/7}$ weeks for deliveries on the estimated due date (EDD) and adjusted by the difference in days between the date of delivery and the EDD for all other births. The EDD is established by ultrasound data or accurately known last menstrual period (LMP), according to ACOG guidelines, as described in the protocol.

Safety outcomes: monitoring of adverse events is described in the protocol.

4. Determination of Sample Size

This study has been terminated due to the advent of the SARS-CoV-2 pandemic in the ChristianaCare population. At study termination, 1,873 subjects were enrolled in the study. To avoid bias in comparison of pre-pandemic controls to prospective subjects who reached term during the pandemic period, the primary analysis of the study will be limited to an estimated 1,453 subjects who reached $37^{0/7}$ weeks gestation before local spread of SARS-CoV-2 in Delaware and the associated shut-down of non-COVID-19 research at ChristianaCare.. Approximately 10,000 historical controls were selected from a period of about 2 years immediately prior to study initiation.

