5.1 Analysis Populations

One control population will be considered in primary analyses: the historical control population. The historical control population includes all subjects who attended ChristianaCare during the eligibility period and who satisfy all eligibility criteria.

The historical control arm will be the control population for primary and alternative analysis of the primary, secondary and exploratory endpoints.

Seven subject populations will be considered in the analyses: an Intent-to-Treat (ITT) population, a modified ITT population, a completer(s) population, a compliant completers population, a non-intervention completers population and a safety population. The completers, compliant completers, non-intervention completers and modified ITT populations are subsets of the ITT population.

The ITT population includes all historical subjects selected and all prospective patients enrolled regardless of whether or not the co-primary outcomes were observed, or in the prospective arm, any PreTRM test result has been generated or intervention consent has been signed. Subjects with missing outcomes will be handled as described in the missing data sensitivity analyses.

The modified ITT (mITT) population includes all subjects for whom both co-primary outcomes are known; and who have either been selected for the historical control group, received a not-higher-risk PreTRM® test result, or consented to and initiated treatment before 24^{0/7} weeks gestation after receiving a higher risk PreTRM® test result.

The completers population includes subjects for whom both of the co-primary outcomes are known, and, in the prospective arm, for whom a PreTRM® test result was generated.

The compliant completers population includes ITT subjects who have missed no more than 20% of daily doses for both low-dose aspirin and vaginal progesterone, and participated in weekly care management calls with no more than 20% missed weeks.

The non-intervention completers population includes all ITT subjects who received a higher-risk PreTRM® test result but neither consented to nor initiated treatment before 24^{0/7} weeks gestation.

The safety population includes all eligible subjects who gave consent to participate in the study and attempted a blood draw for the PreTRM® test, regardless of receipt of study interventions.

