5.3 Covariate Analyses

The prospective participants and historical controls in the study may differ in ways other than the interventions or exposures under investigation. Covariates will be used to adjust the regressions prespecified in the primary analysis for potential differences between the control and prospective arms, and in derivation of propensity scores used to adjust for biases between the two arms, either by weighting subjects in the alternative analysis or by matching subjects in exploratory analyses..

The following variables are candidates for inclusion as covariates in the primary analysis: regression with covariates. These baseline covariates are present before blood draw.

- Maternal age
- Categorical parity: multiparous vs. nulliparous
- Maternal substance use disorders assessed as Neonatal Opioid Withdrawal Syndrome

The following variables are candidates for inclusion as covariates in the alternative analysis using inverse probability score weighting, and in the exploratory analysis using propensity matching. These baseline covariates are present before blood draw.

- Maternal age
- Categorical parity (nulliparous vs. multiparous)
- Gravidity (integer)
- Number of term children
- Number of miscarriages
- Maternal race
- Pre-pregnancy continuous BMI
- Pre-pregnancy categorical low BMI<19
- Maternal height
- Maternal chronic hypertension
- Gestational diabetes
- Insurance status
- Smoking status
- Maternal substance use disorders assessed as Neonatal Opioid Withdrawal Syndrome
- Delivery outside of ChristianaCare

Inclusion of covariates in the covariate-adjusted primary, alternative and exploratory analyses will depend on the proportion of missing values for the covariate, as follows. For each candidate variable, if fewer than 1% of subjects have a missing value, that variable will be included as a covariate in the analysis. Sensitivity of results to missing data will be examined using missing data analysis methods.

The primary and alternative analyses will use cases with complete data for the included covariates, provided that no more than 5% of the total subjects are excluded from the analysis. If more than 5% of the total subjects would be excluded from the analysis,

candidate variables will be dropped from the analyses in order of the percent missing, until no more than 5% of the total subjects are excluded from the analysis.

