5.4 Primary and Alternative Analyses

The primary and alternative analyses will be performed in the modified ITT (mITT) population on the primary, secondary and exploratory endpoints.

The primary analysis is regression with covariates as specified for each endpoint.

The alternative analysis is regression with covariates as specified for each primary, secondary and exploratory endpoint, with weighting by inverse propensity score to address potential selection bias.

Propensity-matched and unadjusted “raw” analyses are pre-specified as exploratory analyses. These analyses will be performed on primary and secondary endpoints.

In analysis combining primary, alternative and exploratory analyses, we will present the demographic and baseline characteristics differing between the prospective arm and historical controls, selected from among the covariates prespecified for the primary and alternative analyses. We will compare the primary analysis using prespecified covariates, the alternative analysis using IPW, and exploratory PSM un-adjusted (raw) data analyses (Table 2). The results from these four distinct methods are expected to show similarity in direction and potentially in magnitude of effect. If differences in direction are observed, further analysis such as double robust propensity score analysis will be conducted.

Variable	Covariate Regression			Inverse Probability Weighted			Matched data			Unadjusted “Raw” data		
	Prospective (N=)	Historical (N=)	p-value	Prospective (N=)	Historical (N=)	p-value	Prospective	Historical	p-value			
Age												
Parity												

Table 2: Baseline Characteristics

For pre-specified analysis populations and for subgroups specified under Subgroup Analyses below, analyses will be conducted to examine the clinically important groups and unbalanced variables between the prospective and historical cohorts.

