5.7 Exploratory Analyses

In AVERT, there is a challenge and opportunity in the moderate rate of acceptance of intervention among high-scoring women in the intervention arm. The exploratory analyses include options for addressing the non-accepting completers in the prospective arm, and comparing them to those in mITT and the compliant completers.

The exploratory outcomes will be summarized within the prospective arm and within historical controls using descriptive statistics and graphical displays where appropriate. Continuous outcomes will be summarized using sample size (n), means, medians, standard deviations, and ranges. Categorical outcomes will be summarized using frequency and percentages. Estimates will be presented with 95% confidence intervals. Exploratory summaries will be performed for the mITT population.

The following exploratory endpoints will be evaluated by a test of proportions in the prospective arm versus historical controls. The null hypothesis is no difference between historical controls and the prospective arm. The alternative hypothesis is relative reduction in proportion of occurrence of one or more conditions in the prospective arm as compared to historical controls. Statistical testing for these endpoints will be performed using a logistic regression model with covariates as specified above for the primary analysis, and with propensity scoring adjustment as specified for the alternative analysis.

- Reduction in occurrence of one or more major neonatal morbidities with high likelihood of major chronic illness (MNM): cystic periventricular leukomalacia,

- grade 3 and 4 intraventricular hemorrhage, grade 3 or higher retinopathy of prematurity, bronchopulmonary dysplasia.
- Reduction in the rate of PTB <35 weeks, <32 weeks and <37 weeks of gestation. This analysis will be repeated for premature neonates delivered after spontaneous rupture of membranes or spontaneous onset of labor with gestational age at birth <32, <35 and <37 weeks vs. all other neonates.
- Reduction in NICU admission rates in the immediate neonatal period prior to initial discharge or neonatal death. This analysis will be repeated for all premature neonates, and for premature neonates delivered after spontaneous rupture of membranes or spontaneous onset of labor.

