As an exploratory analysis, a test of the proportional odds assumption for NMI data will be conducted. If the proportional odds assumption does not hold, we will examine the data using a set of separate logistic regressions or partial proportional odds models, to explicitly see how the odds ratios for the explanatory variables vary at the different thresholds. Alternatively, we will also apply the generalized logit model, which treats the response as nominal (unordered) rather than ordinal and has a full set of parameters for each generalized logit. We will then compare the results from proportional, fully nonproportional, and partial proportional odds models fitted to data.

As exploratory analyses, the primary analysis will be replicated, with the modification that the analysis will be restricted to prospective subjects with at least one propensity-matched control, and historical controls will be restricted to those propensity-matched to prospective subjects. At most 4 historical controls will be matched to each prospective subject. Matching algorithms will be chosen from among nearest neighbor matching, caliper matching with comparison units within a certain width of the propensity score of the treated units get matched, where the width is generally a fraction of the standard deviation of the propensity score; Mahalanobis metric matching in conjunction with propensity score matching (PSM), stratification matching, difference-in-differences matching (kernel and local linear weights), or exact matching. The matching method will

be chosen by the distribution of the propensity scores and the balance status of baseline characteristics.

As exploratory analyses, the primary and alternative analyses will be replicated using the ITT population. Subjects with missing data for required variables will be excluded from the analyses. To test if covariates are known to be misclassified under some approaches, an “intention to treat” analysis will be conducted that assumes that each participant continues to be exposed once they have received an initial treatment. Originally used in the analysis of randomized trials, this approach has been used in this hybrid study. It can be worthwhile to do a sensitivity analysis on studies that use an “intention to treat” approach to see how different an “as treated” analysis would be even if intention to treat is the main estimate of interest.

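### The mITT set requires both co-primary outcomes to be known, so the primary and alternative analyses of every endpoint drop women whose own endpoint is recorded

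*SAP*

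**What the plan says.** Section 5.1 sets the outcome condition: "The modified ITT (mITT) population includes all subjects for whom both co-primary outcomes are known". Its other conditions concern membership of the historical group, the test result, and consent to and start of treatment. The completers population carries the same both-known condition.

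Section 5.4 applies the set to everything: "The primary and alternative analyses will be performed in the modified ITT (mITT) population on the primary, secondary and exploratory endpoints".

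The endpoints need different records (sections 3.7 and 5.7):
- Gestational age at birth starts from 40 weeks at the due date and is "adjusted by the difference in days between the date of delivery and the EDD for all other births". It needs the delivery date and the EDD only.
- The exploratory preterm-birth endpoint, "Reduction in the rate of PTB <35 weeks, <32 weeks and <37 weeks of gestation", needs nothing more.
- NNOLOS needs the date of discharge home: "This includes all levels of care before discharge home, including all transfers across levels of care".
- NMI needs the component diagnoses, the NICU days and the mortality status.

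One population is free of the condition and is also used for the endpoints against historical controls. ITT keeps subjects "regardless of whether or not the co-primary outcomes were observed", and section 5.7 says: "As exploratory analyses, the primary and alternative analyses will be replicated using the ITT population".

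**The concern.** Each endpoint's main analysis depends on how complete the records are for other endpoints. A preterm birth with a known date does not count if the neonatal discharge date is missing. An infant whose NMI is fully established leaves the NMI test if NNOLOS is missing, and the reverse also holds.

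Nothing in the plan needs this. Section 2 gives the purpose of mITT as comparing women who fully consented to the strategy with women under standard care. The arm, test-result and treatment conditions achieve that without the outcome condition. Holm's method (section 5.4 onwards, under the primary endpoints) combines two separately obtained p-values.

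If the loss is equal in both arms, some precision is lost. If it differs by arm and is related to prematurity, it biases the comparison. The arms are assembled differently: controls are found retrospectively in the hospital's database, while prospective women are enrolled at 19-20 weeks and followed forward. Unequal completeness is therefore possible. Primary and secondary tests are one-tailed (section 5), so a bias towards benefit would matter most.

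**Working it through.** **1. Which women are affected**

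| Endpoint | Records it needs | Further condition imposed by mITT |
|---|---|---|
| Gestational age (secondary) | delivery date, EDD | NMI and NNOLOS known |
| Preterm-birth rates (exploratory) | delivery date, EDD | NMI and NNOLOS known |
| NMI (co-primary) | diagnoses, NICU days, mortality | NNOLOS known |
| NNOLOS (co-primary) | dates of birth and discharge home | NMI known |

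**2. Do the plan's other provisions recover them?**
- *ITT replication (5.7).* It is exploratory. It excludes subjects with missing required variables without saying whether that is judged per endpoint, whereas 5.1 refers missing ITT outcomes to missing-data sensitivity analyses. ITT also includes untested women and those who did not accept intervention, so a difference from mITT could not be traced to the both-known rule.
- *Check on completers excluded from mITT (5.7).* Completers already have both co-primaries known, so this check cannot see the loss.
- *The 5% cap on exclusions (5.3).* It concerns missing covariates. No cap applies to missing outcomes.
- *Multiple imputation (5.7).* It is described for candidate covariates.
- *Section 5.10.* It compares counts of missing values between arms. That could reveal a difference but does not repair it.

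**3. The plan's own power figure, for context**

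Inputs from section 4: 1,453 prospective women, 34% screen-positive, 55% compliance, 10,000 controls, NMI ≥ 3 in 0.020-0.023 versus 0.036. Taking compliance as the share of higher-risk women who enter mITT:

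mITT size = 1,453 × (0.66 + 0.34 × 0.55) = 1,453 × 0.847 = 1,231.

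At one-sided 0.025 (first Holm step), power for NMI ≥ 3 is 0.680 to 0.883, which rounds to the stated 0.7-0.9.

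If a share of both arms lacks a co-primary outcome (assumed, since the SAP gives none), power becomes:

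| Missing | NMI, 0.023 vs 0.036 | NMI, 0.020 vs 0.036 | NNOLOS, HR 1.32* |
|---|---|---|---|
| 0% | 0.680 | 0.883 | 0.828 |
| 2% | 0.670 | 0.875 | 0.820 |
| 5% | 0.654 | 0.863 | 0.809 |
| 10% | 0.628 | 0.842 | 0.787 |

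*Events taken as the top 10% of stays.

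These losses are upper limits on what the fix could recover for a co-primary, because some of the women will lack that co-primary itself.

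**4. Bias in preterm birth**

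Assumptions: a share d of prospective women, and no controls, has a known gestational age but an incomplete co-primary; their preterm rate is r × 9.1%; the intervention has no effect.

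Retained rate = 0.091 × (1 − d·r)/(1 − d)

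SE of the difference = √[0.091 × 0.909 × (1/1,231 + 1/10,000)] = 0.0087

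| d | r | Retained rate | False relative reduction | In SE |
|---|---|---|---|---|
| 2% | 1.5 | 0.091 × 0.97/0.98 = 9.0% | 1.0% | 0.1 |
| 2% | 3 | 0.091 × 0.94/0.98 = 8.7% | 4.1% | 0.4 |
| 6% | 1.5 | 0.091 × 0.91/0.94 = 8.8% | 3.2% | 0.3 |
| 6% | 3 | 0.091 × 0.82/0.94 = 7.9% | 12.8% | 1.3 |

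The share of recorded preterm births discarded is d·r, or 3% to 18%. Of about 1,231 × 0.091 = 112 prospective preterm births, that is about 3 to 20.

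If both arms have the same d and r, the factor (1 − d·r)/(1 − d) cancels from the ratio of rates and no bias arises.

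**The case against.** The strongest reply is that the effect may be negligible. Section 5.10 expects few missing values for most variables, the power loss at 2-5% missing is slight, and the preterm example loses women from one arm only, all in one direction, on an exploratory endpoint. A common set for two co-primaries is also partly a matter of preference. All of this stands as a limit on size. It does not give a reason for the rule, which discards recorded data without a stated benefit.

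A reader might also infer more than the SAP supports:
- *That these women enter no analysis at all.* They can enter the exploratory ITT replication, and the compliant-completer, non-intervention and safety definitions carry no outcome condition.
- *That the losses are mostly transfers and outside deliveries, hence the sickest infants.* The SAP does not say who will lack an outcome. Transfers across levels of care count within NNOLOS, and "Delivery outside of ChristianaCare" is a candidate covariate for the alternative analysis (5.3), so such births are expected among those analysed.
- *That deaths are lost.* Stillbirth or death before discharge sets NNOLOS to one day beyond the longest stay, so it is known. NNOLOS is also truncated at 44 weeks, so an infant still in hospital then needs no discharge date.
- *That more than 20 NICU days makes NMI known.* Level 3 requires no perinatal mortality, Appendix I counts neonatal death to 28 days, and the ordinal model separates levels 3 and 4. Admitting partial records once level 3 is reached would bring in severe infants while milder infants with equally partial records stayed out. Inclusion would then depend on the outcome.

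**Conclusion.** The point holds for the primary and alternative analyses of all endpoints. It is clearest for gestational age and the preterm-birth rates, which need neither co-primary. For NMI and NNOLOS it holds only for women in whom that endpoint is fully determined and the other is missing.

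The size is unknown. Section 4 names retention as a factor but gives no figure, and the power statement counts 1,453 prospective subjects as having outcomes. Under the assumed one-arm loss, the false relative reduction in preterm birth is 1-13%, or 0.1-1.3 standard errors. If controls lost more than prospective women, the bias would run the other way. With equal loss only precision suffers, and with almost complete records nothing changes. It is worth correcting because the correction is simple and uses data already collected, not because a large distortion has been shown.

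**What to change.** In section 5.1, define mITT and completers by arm, test result and (for mITT) treatment initiation, and remove the condition that both co-primaries be known. In section 5.4, state the inclusion rule for each endpoint within that population:
- Gestational age and preterm-birth rates: all members with a known delivery date and EDD.
- NNOLOS: all members for whom it is determined under the section 3.7 rules.
- NMI: all members whose level is fully ascertained, with the same completeness rule for every level. A partial record does not count as known merely because level 3 has been reached.

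Report N per endpoint and arm, with the number not determined. Keep the both-known set as a sensitivity analysis. State whether required variables in the ITT replication are judged per endpoint.

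The cost is SAP wording and slightly different denominators between endpoints, which the tables must show. No new data are needed.

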The AVERT study addresses an enormous obstetrical problem having a large unmet need with the use of a novel risk assessment tool (PreTRM®) and established multimodal interventions administered within the single ChristianaCare hospital network. However, there are several potential limitations to the AVERT study. Comparisons to historical controls can be susceptible to selection bias and epoch effects. Subjects who don't accept interventions may add self-selection bias. As well, AVERT is subject to a research halt due to the spread of SARS-CoV-2, avoiding a pandemic epoch effect while restricting study size.

This statistical analysis plan addresses the study objective of evaluation of the PTB prevention strategy while overcoming potential study limitations. The original endpoints are replaced with more powerful endpoints aligned to the study size and faithful to the study's goal of reducing adverse outcomes. The primary analysis is in a modified ITT population enabling comparison of the fully consented PTB prevention strategy population to a population who received standard care. To adjust for any bias in consent to intervention, exploratory analyses compare subjects accepting and not accepting interventions, and address the efficacy of individual intervention components.

An estimated 1,453 prospective subjects reached a gestational age of $37^{0/7}$ weeks before local spread of SARS-CoV-2 in Delaware and the associated shut-down of non-COVID-19 research at ChristianaCare. Approximately 10,000 historical controls were selected

from a period of about 2 years immediately prior to study initiation. The study design shows at least 86% power for 5% alpha shared across two co-primary endpoints: neonatal morbidity and mortality index and neonatal length of total hospital stay.

The funder, Sera Prognostics, will remain blinded to all clinical data until a formal communication of topline results from this analysis is made.

Background: Preterm birth (PTB) remains the leading cause of neonatal mortality and long term disability throughout the world. Recently treatments early in pregnancy such as progesterone, cervical support and maternal support have been demonstrated to delay delivery amongst at risk women. Nonetheless, the majority of women who are at risk are not identified using current screening modalities.

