As exploratory analyses, the primary and alternative analyses will be replicated using the completers population with treatment covariates. Covariates for treatment modalities inclusive of use of aspirin or progesterone, will be included in the analyses if showing record of use between LMP and delivery in both the prospective arm and historical controls. Subjects with missing data for required variables will be excluded from the analyses. Subjects in the higher-risk group accepting interventions will be compared to non-intervention completers and to historical controls using descriptive statistics as described above. If use of any treatment is significantly associated with variables specified for the alternative analysis, this analysis will be repeated with inclusion of such variables as covariates in the analysis. Subjects with missing data for required variables will be excluded from this analysis.

As an exploratory analysis, the primary and alternative analyses will be replicated using the compliant completers population plus the not-higher-risk group as the preterm prevention arm for comparison to historical controls. Additional subgroup analysis of the compliant completers population will apply the primary, secondary and exploratory endpoints to subjects compliant with each component of the intervention versus all other compliant completers, and versus non-intervention completers. If compliance with any

treatment is significantly associated with variables specified for the alternative analysis, this analysis will be repeated with inclusion of such variables as covariates in the analysis. Subjects with missing data for required variables will be excluded from this analysis.

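### Higher-risk women who consented but did not start treatment before 24 0/7 weeks are in neither the treated mITT group nor the non-intervention completers, so the exploratory acceptance contrasts omit them

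*SAP*

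**What the plan says.** Four definitions in SAP Section 5.1 matter here.

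- **mITT, higher-risk part:** both co-primary outcomes known, and the woman "consented to and initiated treatment before 24^{0/7} weeks gestation after receiving a higher risk PreTRM® test result".
- **Non-intervention completers:** ITT subjects with a higher-risk result who "neither consented to nor initiated treatment before" 24 0/7 weeks. No condition on known outcomes is attached.
- **Completers:** those "for whom both of the co-primary outcomes are known, and, in the prospective arm, for whom a PreTRM® test result was generated". Consent and start of treatment play no part.
- **Compliant completers:** "ITT subjects who have missed no more than 20% of daily doses for both low-dose aspirin and vaginal progesterone", with a similar limit on missed care-management calls. There is no 24-week condition.

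The Section 2 executive summary says that, to deal with bias in consent, "exploratory analyses compare subjects accepting and not accepting interventions". Section 5.7 opens by promising "options for addressing the non-accepting completers in the prospective arm, and comparing them to those in mITT and the compliant completers". It then specifies: "Subjects in the higher-risk group accepting interventions will be compared to non-intervention completers and to historical controls". The same section uses non-intervention completers as comparator twice more: in the component-by-component compliance subgroups, and in the re-assessment of the risk-score discontinuity.

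**The concern.** The mITT population carries the primary analysis, and it removes higher-risk women according to what they did after the test result. Section 6.1 accepts that bias from incomplete acceptance cannot be directly adjusted against the historical controls, because they have no PreTRM score. Comparisons within the prospective arm are therefore the direct way to see how the women removed differ from those kept.

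For that purpose the comparator should contain every higher-risk woman with known outcomes whom mITT leaves out. As worded, it contains only those who failed both conditions. Women who agreed to treatment and then did not start in time may differ from outright decliners and from starters. The contrasts as defined cannot show whether they do.

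Two looser points add to this. The word accepting in Section 5.7 is not defined. If it means consented, these women move to the accepting side although mITT excludes them. And the group is called completers without requiring the outcomes that make a completer.

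**Working it through.** No figure in the SAP bears on this point, so the check is one of logic. Take a higher-risk woman with both co-primary outcomes known and classify her by consent and by start of treatment before 24 0/7 weeks.

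| Consented | Started before 24 0/7 weeks | Treated mITT | Non-intervention completers |
|---|---|---|---|
| Yes | Yes | Yes | No |
| Yes | No | No | No |
| No | Yes | No | No |
| No | No | No | Yes |

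The mITT rule is A and B. Its complement is (not A) or (not B). The SAP wrote (not A) and (not B), which leaves rows two and three unclassified. Row three, a start without consent, is mainly theoretical. Row two is an ordinary possibility when a treatment bundle is offered.

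**Late starters.** A woman who consented before 24 0/7 weeks and started afterwards is in row two, hence in neither group. If the time limit is read as governing consent as well as start, a woman who did both after 24 0/7 weeks already meets the non-intervention wording. Because compliant completers has no time limit, she could also be a compliant completer if she adhered. Overlap is thus possible under the present text.

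**Where the row-two women still appear.**

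- *ITT replication (Section 5.7):* included when the required data are present, but pooled with the whole prospective arm.
- *Completers replication with treatment covariates (Section 5.7):* included when both outcomes are known, again pooled. Use is counted over the whole span from last menstrual period to delivery, so a late starter would count as a user.
- *Check on completers excluded from mITT (sensitivity analyses in Section 5.7):* covers them, but asks whether exclusion is associated with the baseline variables of the alternative analysis. It does not compare outcomes.

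**Where they are missing as untreated comparators.** The comparison of accepters with non-intervention completers, the component-compliance subgroups, and the risk-score re-assessment of compliant against non-intervention completers.

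**Does the repair close the gap?** A higher-risk result implies that a test result was generated, so higher-risk completers are all higher-risk women with both outcomes known. Splitting them into A-and-B and not(A-and-B) puts every row of the table in exactly one group.

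**The case against.** The best defence has four parts.

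1. *The women are not lost to the plan.* This is correct. A reader might infer from the definitions that they disappear from every check on acceptance bias. The ITT and completers replications and the exclusion check show otherwise. What stands is narrower: none of those isolates their outcomes against the treated group.

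2. *A never-consented, never-started group is a clean untreated contrast, and the complement would bring late-treated women into a group named non-intervention.* This has force. It does not rescue the present wording, which can already admit a woman who first consented and started after 24 0/7 weeks. It does mean that late starters must be shown separately.

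3. *The absent known-outcome condition does little harm.* Largely so: Section 5.7 drops subjects with missing required data from the related analyses, and the name signals the intention. It is a matter of tidying.

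4. *The affected analyses are exploratory.* Correct. No confirmatory test depends on this group.

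A reader might also infer that the gap hides pregnancies that ended before treatment could begin. The SAP does not support that as a consequence of this definition. Appendix I counts fetal demise only at a viable gestational age, so an earlier loss may have no scored outcome and would be left out under either wording.

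**Conclusion.** The two definitions are not complements. Higher-risk women who consented but did not start before 24 0/7 weeks are missing from the Section 5.7 contrasts that rely on non-intervention completers. This is a minor defect, confined to exploratory analyses, and it leaves the co-primary tests as they are.

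Its size cannot be stated. A reader might try to derive a count from the Section 4 planning figures: 1,453 prospective subjects, 34% higher-risk, 55% compliance. The first two give 1,453 × 0.34 = 494 higher-risk women, but the next step fails. Section 4 uses the 55% for complying with the interventions, which is not the same as consenting and starting by 24 0/7 weeks. A woman who started in time and later stopped is non-compliant yet inside mITT. Nor does the SAP say what share of the women outside mITT had consented, or whether their risk was higher or lower. Neither the number in the gap nor the size or direction of any bias follows from the document.

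The conclusion rests only on reading the Section 5.1 wording literally.

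**What to change.** In Section 5.1, define non-intervention completers as higher-risk completers (both co-primary outcomes known) who did not both consent to and initiate treatment before 24 0/7 weeks. In Section 5.7:

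- Show the group in separate rows: never consented, consented but never started, and late starters.
- Define accepting as membership of the higher-risk part of mITT.
- State a rule that makes the comparator and compliant completers mutually exclusive, so that a late starter is not counted on both sides of a contrast.

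This changes a few phrases and no clinical rule. It uses dates of consent and treatment start, which are already needed to apply the mITT definition. The cost is slightly more tabulation, and a less clean untreated comparator if late starters are pooled with the rest. The separate rows let a reader see the result with and without them.
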